4. OVERALL STUDY DESIGN

4.1 Study Design

This is a prospective cohort, single-center, open-label study in subjects with chronic lower extremity wounds. The study will enroll up to 20 subjects. Subjects will undergo screening evaluations to determine eligibility to enroll in the study. All study subjects will receive micro water jet technology debridement as opposed to other debridement methods as part of their wound care treatment. The other aspects of subjects wound care protocol will remain unchanged. In the case of bilateral limb ulcers, or multiple ulcers, subjects will have the option to receive micro water jet debridement on one or all of the ulcers.

Clinical efficacy analyses will include assessment of changes in the extent and size of ulcers, percentage healing and rate of healing, leg rest pain score using VAS scale, pain experience during debridement using VAS scale, incidence of wound infection (See Section 3).

Safety assessments, including AE reporting, physical examination, vital sign measurements, concomitant medications will be performed at all clinical visits throughout the study.

4.2 Study Duration

Up to 20 weeks, sooner pending wound healing as defined by 100% re-epithelialization.

5. STUDY PROCEDURE

5.1 Recruitment

Patients will be recruited by the study investigators and by research coordinators at the Rosalind Franklin Health Clinic. Patients will be invited to participate and the investigator or research staff will discuss the study design, duration and risks of participating in the study. The subject will then be provided with a consent form to read at their leisure. The investigator or research coordinator will be available to answer questions and provide more explanation as requested by the potential study subject and their family.

5.2 Informed Consent

Informed consent will be obtained by the study coordinator prior to any screening measures. Discussion of the study will be done in a private room. The subject will be allowed to read the consent at their leisure and discuss it with family members before they make a decision. If the patient agrees to participate, we will provide them with a copy of the consent, a copy will be placed in the medical record and a copy will be placed in the patient's study folder.

5.3 Study Participants

20 patients with chronic lower extremity ulcers will be recruited for this prospective cohort at the Rosalind Franklin Health Clinic to receive micro water jet technology debridement as part of their wound care treatment plan after being informed of the study and providing informed consent

Inclusion Criteria and Population:

- a) Male or female age 18 or older
- b) The ability and willingness to provide Informed consent
- c) Presence of a chronic lower extremity ulcer
 - Chronic ulcer is defined as that $\prod 4$ weeks in duration.
 - Subject's informed consent for participation prior to proceeding with micro water jet technology debridement
- d) Patient's ulcer cannot exhibit any gross clinical signs of infection.
- e) Patient is willing to participate in all procedures and follow up evaluations necessary to complete the study.
- f) Patient willing and able to comply with having micro water jet technology debridement potentially weekly or biweekly as part of their wound care treatment plan for up to 20 weeks. Exclusion Criteria:
- a) Patients with active wound infection, or untreated osteomyelitis
- b) Patients with dementia, or impaired cognitive function
- c) Patients who are unable or unwilling to participate in all procedures and follow up evaluations
- d) Patient has Active Charcot foot
- e) Patient with malignant wounds

5.4 Subject events after entry:

Screening/Pre-debridement:

Subjects will be screened to ensure that they meet the inclusion and exclusion criteria. The study will be explained and written informed consent obtained from each patient prior to the initiation of screening procedures.

Following the screening, subjects will receive baseline evaluation/assessment as part of the general clinic visit and treatment initiation. Baseline evaluation/ assessment will include recording of clinical observations.

Clinical Observations and Recording:

1. Wound size and appearance:

Wound dimensions, locations, and characteristics will be documented prior to commencement of the study and assessed weekly or biweekly. Ulcer assessments include wound measurement, photographs, proportion of granulation tissue, and dressing changes.

2. Physical exam:

Physical exam will be conducted, including vascular, dermatological, deformities and range of motion, neurological, and infection assessments, as part of a regular wound care visit.

Medical History: A detailed medical history will include: previous history, location and duration of previous ulcers, amputation (toe, foot, below knee, above knee), lower extremity bypass, lower extremity angioplasty, CABG, cardiac angioplasty, last visit by physician (in weeks), and current/past use of special shoes or insoles.

Neurological Evaluation: The Neurological assessment will consist of Vibratory Perception Threshold testing (VPT) using the technique described by Young¹², and the 10 gram Semmes-Weinstein monofilament using the criteria described by Armstrong and Lavery¹³. The presence of sensory neuropathy will be identified as vibratory perception threshold greater than 25 volts or inability to accurately perceive a 10 gram Semmes-Weinstein monofilament at 1 or more of 10 test sites on the sole and dorsum of the foot.

Vascular Assessment: The vascular assessment will consist of palpation of the dorsalis pedis and posterior tibial arteries and non-invasive Doppler studies. Ankle Brachial Index (ABI) will be performed of both extremities.

Deformities & Joint Range of Motion: Range of motion of the ankle, subtalar and first metatarsophalangeal joint will be assessed using standard landmarks and procedures. We will define hallux rigidus as first metatarsophalangeal joint dorsiflexion less than 65 degrees. Toe and metatarsophalangeal joint deformities will be defined as present when a rigid, non-reducible deformity exists.

Wound Classification: The site investigators will evaluate the wounds. Wounds will be classified according to the University of Texas Wound Classification System (Table 1). Although this classification system was originally described for diabetic foot ulcers, this the only validated wound classification system and will be adapted for the purpose of this study.¹⁴

Table 1: The University of Texas Diabetic Wound Classification System^{14, 15}

	0
A	Pre orpos tul cerative lesion
A.	com pletelye pithelialized
	Pre orpos tulcerative lesion,
В	completelyepithe lializedwith
	infe ction

I				
Supe rficial wound, not	i nvol	vi ng		
te ndon, c aps ul e, orbone				
Superficial wound, not	i nvol	vi ng		
tendon, c a psule, orbone with				
infe ction				

Grade

Wound pe	netratingt ot endo
	orc aps ul e
Wound pe	netratingt ot endo
ore an	sule with infection

3. Monitoring diabetic control (where appropriate):

No specific attempts to improve glucose control will be made during the study by the investigators. Glucose control will not be used as an exclusion criterion. We feel that this more accurately reflects the diabetic foot ulcer population. Consultations to primary care physicians and sub specialist will be provided as needed. Patients will be encouraged to control their diabetes as well as they can and to contact their usual care provider for symptomatic hyperglycemia, hypoglycemia or other diabetes-related problems. Any changes in diabetes management will be recorded. Patients will monitor their diabetes control in their usual manner.

4. VAS pain scale:

Patient's pain associated with the ulcer will be assessment and documented via the VAS pain scale. Patient's pain and subjective comments associated with micro water jet technology debridement will also be assessed and documented.

5.5 Treatment

Following base assessment, the wound will be debrided using micro water jet technology. An initial test of sterile saline will be sprayed onto the patient's hand so the patient can get a feel for the force of the water jet and know what to expect. Topical analgesic (lidocaine) will be administered to the wound area prior to debridement as needed. Micro water jet technology will be used to remove all devitalized, necrotic tissue and until extremely fine bleeding develops. A protective shield will be used to prevent spread of the aerosol formed after the stream of sterile saline comes into contact with the wound (Figure 4). Both the hand piece delivering the sterile saline stream and the protective shield are one-time use disposable items. Treatment times will be dependent on the wound size and level of contamination. A previously published retrospective study noted the treatment duration to be between 1 and 22 minutes utilizing 100-200mL of sterile saline as rinsing fluid¹¹. Hemostasis will be controlled via pressure. Appropriate wound dressings will then be applied. Caution will be used in patients with uncontrolled hypertension and patients on anticoagulation therapy or acetylsalicylic acid medication. While debridement is not contraindicated in these patients, there may be a higher risk of excessive bleeding. Compression will initially be used to control hemostasis followed by an alginate or a hemostyptic agent.

Figure 4.

Debridement of wound using micro water jet technology. A protective shield is used to prevent the spread of the aerosol formed after the stream of sterile saline comes into contact with the wound.

5.6 Subsequent visits

Patients will return to clinic every one to two weeks (+/- 2 days) as part of their regular wound care treatment plan for follow up assessment including wound evaluation and photograph. Wounds will be subsequently debrided using micro water jet technology if deemed appropriate by the investigators followed by a dry sterile dressing as previously described. Wound will be followed for a total of 20 weeks or when the wound has completely healed, as defined by 100% re-epithelialization.

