3. STUDY END POINTS

3.1 Primary Endpoints

The primary endpoints are to explore clinical efficacy and include:

- 1. The extent and size of ulcers (summation of the products of the long x short axis for all ulcers measured in centimeters squared, plus ulcer depth) will be evaluated and photographs of ulcers taken during screening and on all clinic visits up to 20 weeks or when the ulcer is healed, whichever is sooner.
- 2. Leg rest pain score visual analogue scale (VAS) graded from 0 (pain free) to Grade 10 (maximum pain) during screening and on all clinic visits up to 20 weeks, or when the ulcer is healed, whichever is sooner.
- 3. Pain during Debridement score VAS graded from 0 (pain free) to Grade 10 (maximum pain) during on all clinical visits when debridement is performed for up to 20 weeks, sooner pending wound healing.
- 4. Subjects feedback regarding their debridement experience with micro water jet technology will be collected on all clinical visits when debridement is performed.
- 5. Incidence of wound infection.

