5.7 End of study visit

At the end of the 20-week evaluation, patients with open wounds will return to clinic on Day 112 (+/- 2 days) for the end of study visit. In cases of complete wound healing or patient withdraw, the end of study evaluation will take place at the patient's last day of study visit and will occur prior to Day 112. The following assessments will occur at the End of study visit:

- 1. Wound evaluation and photograph
- 2. VAS pain scale
- 3. Wound debridement (if applicable)

A wound dressing, if deemed necessary by the investigator will be applied.

5.8 Adjunctive Care:

All patients will receive standard adjunctive therapy for lower extremity ulcerations. Efforts will be made to control any edema by limb elevation, diuretic medication or compression hose, as indicated. Patients will be advised to stay off the affected foot as much as possible, and asked to avoid walking, except as absolutely necessary. Patients will be offered other assistive modalities at the time of enrollment (crutches, canes, and walkers) to enhance postural stability.

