8.2 Data Analysis

Data analysis will include descriptive statistics and Chi-square and Fisher's exact tests for categorical variables. Continuous variable will be assessed using the Student t test, and where possible linear regression models. Outcomes variables will be compared with repeated measures of analysis of variance tests. Statistical significance will be accepted for p values <.05.

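### Debridement pain is scored only when the investigator debrides an open wound, which standard repeated-measures ANOVA handles poorly; use a mixed model on all scores and report who was debrided

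*Combined protocol and SAP*

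**What the plan says.** Section 5.5 has every subject treated at the start: "Following base assessment, the wound will be debrided using micro water jet technology". From then on Section 5.6 leaves the choice to the investigators: "Wounds will be subsequently debrided using micro water jet technology if deemed appropriate by the investigators". Section 5.7 makes debridement at the end-of-study visit conditional as well.

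Section 3.1 lists pain during debridement as item 3 of the primary endpoints, scored on a 0 to 10 VAS "during on all clinical visits when debridement is performed for up to 20 weeks, sooner pending wound healing". Follow-up ends at healing: "Wound will be followed for a total of 20 weeks or when the wound has completely healed".

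Section 8.2 names descriptive statistics, tests for categorical data, the t test and, where possible, linear regression. It then says: "Outcomes variables will be compared with repeated measures of analysis of variance tests". The threshold is "Statistical significance will be accepted for p values <.05". The plan gives no analysis time points, no missing-data rule, no criterion for when debridement is appropriate, and no rule for a visit at which none is done.

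**The concern.** A debridement-pain score needs two things at a follow-up visit: a wound that is still open and a decision to debride it. Both are related to how the wound is doing.

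Two problems follow. First, repeated-measures ANOVA in its standard form drops any subject with a gap. It would exclude everyone who heals before the last analysed visit and everyone who misses one debridement. Second, if all available scores are averaged by visit instead, the mean at a late visit describes a different and selected set of subjects from the mean at the first. A change between the two can then reflect who is still being debrided rather than how much debridement hurts.

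The study has a single open-label arm, so no comparator would expose such an artefact. The Introduction presents little or no pain as an advantage of the technology, so a change in the pain curve is likely to be read as a finding.

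**Working it through.** **The plan's own figure.** Section 8.1 takes 16 evaluable subjects and 20% loss: 16 / (1 − 0.20) = 20, which matches the stated enrolment. No effect size, SD or power is given, so nothing else can be reproduced. The figure of 16 is used below.

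**Number of follow-up visits, k.** Section 5.6 sets visits one to two weeks apart.
- Two-weekly visits give k = 9 after the first treatment in a series of ten visits, or k = 10 if a week-20 visit is counted as well.
- Weekly visits over 20 weeks give k = 20.
- Section 5.7 says "patients with open wounds will return to clinic on Day 112 (+/- 2 days) for the end of study visit". Day 112 is week 16, whereas 20 weeks is Day 140. Ending at Day 112 gives k = 8 or 16. Sections 5.6 and 5.7 must be reconciled before the number of repeated measures can be fixed.

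**Chance of debridement at each follow-up, p.** The documents do not give it. The range 70% to 95%, and independence between visits, are assumptions.

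**Expected subjects with a complete series** = 16 × p^k, before any loss to healing:

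| k | p = 0.70 | p = 0.80 | p = 0.90 | p = 0.95 |
|---|---|---|---|---|
| 8 (two-weekly, Day 112) | 0.9 | 2.7 | 6.9 | 10.6 |
| 9 (two-weekly, ten visits in all) | 0.6 | 2.1 | 6.2 | 10.1 |
| 10 (two-weekly, 20 weeks) | 0.5 | 1.7 | 5.6 | 9.6 |
| 16 (weekly, Day 112) | 0.05 | 0.4 | 3.0 | 7.0 |
| 20 (weekly, 20 weeks) | 0.01 | 0.2 | 1.9 | 5.7 |

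For example, 0.9^9 = 0.387, and 16 × 0.387 = 6.2.

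**Healing.** If 30% healed before the end (an assumption), at most 16 × 0.70 = 11.2 subjects could be complete. With p = 0.90 and k = 10 the expected number is 11.2 × 0.349 = 3.9.

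**Selection.** A simulation with no true change in pain used 20 subjects, 10 visits, subject means drawn from a normal distribution with mean 4 and SD 2 limited to 0–10, within-subject SD 1, a 70% base chance of debridement, and 4,000 runs. The log-odds of debridement depended on the last recorded pain score. The mean at first debridement was about 4.0.

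| Change in log-odds per pain point | Mean at last visit |
|---|---|
| 0 | 4.0 |
| −0.25 | about 3.8 |
| −0.5 | about 3.5 |
| +0.25 | about 4.3 |
| +0.5 | about 4.6 |

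The drift is 0.3 to 0.6 points either way, and its sign is the sign that was assumed.

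**Does a mixed model help?** With the negative slopes and 4,000 subjects, a random-intercept model estimated the change from first to last visit as zero to within 0.01 (SE 0.02). The raw means still fell. The model succeeds here because the simulated decision depends only on pain already recorded.

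**The case against.** Section 8.2 is generic. It does not tie repeated-measures ANOVA to debridement pain in particular, does not make every visit a factor level, and does not prescribe complete-case handling. Descriptive statistics, which it also names, would keep every score. This stands in part: the loss of subjects is a property of the standard method applied across all visits. But debridement pain is a listed primary endpoint, the method is named for outcome variables without exception, and no smaller set of time points is given.

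A reader might infer that only a handful of subjects must remain. The documents do not support that. They give no debridement rate, and the Introduction itself expects chronic wounds to need repeated debridement, so 95% is plausible; about 10 of 16 would then remain with two-weekly visits, before healing.

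A reader might also infer that the selection makes pain appear to fall. Nothing in the plan makes pain a reason to withhold debridement. Section 5.5 ties it to devitalised tissue and allows topical lidocaine, and reversing the assumed dependence reverses the drift.

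The simulated drift is also about one standard error of a last-visit mean (roughly 0.57) or less, which is small for a pilot. That stands, and it limits the severity. Finally, conditional scoring is intrinsic to this endpoint, and a mixed model does not remove selection on unrecorded factors. Both are true; they are reasons to state the assumption and show the counts, not to keep the ANOVA.

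**Conclusion.** The point holds as a mismatch between an endpoint that is intermittent by design and a method that in its standard form needs complete series. The named method excludes all early healers and anyone who misses a debridement at an analysed visit. With nine two-weekly follow-ups that leaves about 0.6, 2.1 or 6.2 of 16 subjects at 70%, 80% or 90% debridement per visit; at 95% with ten follow-ups it leaves about 10, before healing losses. These sizes rest on assumed debridement rates, independence between visits, and ANOVA run over every visit.

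Later means come from a selected subset whichever rate applies. The direction of any bias cannot be determined from the documents, and no claim is made that the planned analysis favours the device. The sample size of 20 is not affected. The change should be made, but it does not undermine the study.

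**What to change.** In Section 8.2:
1. For debridement pain, replace repeated-measures ANOVA with a linear mixed model: time since first debridement as fixed effect, subject as random effect, all recorded scores used. This also copes with weekly and two-weekly visits that share no common grid.
2. State that the model is valid only if the decision to debride depends on recorded data that the model takes into account.
3. Tabulate by visit the number of subjects debrided and, for the rest, the reason (for example healed, clean wound, pain, withdrawn).
4. State that a change in raw visit means will not be read as a change in pain.
5. Report the VAS at the first study debridement, for all treated subjects, with a 95% CI. By Section 5.5 this score does not depend on a later choice to debride. It belongs beside the longitudinal result and should not replace it, because Section 3.1 defines the endpoint over all debridements and one first exposure does not describe repeated treatment.

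The cost is slightly more analysis work and one reason code per visit. No visits are added, and no clinical decision about debridement changes.

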5.7 End of study visit

At the end of the 20-week evaluation, patients with open wounds will return to clinic on Day 112 (+/- 2 days) for the end of study visit. In cases of complete wound healing or patient withdraw, the end of study evaluation will take place at the patient's last day of study visit and will occur prior to Day 112. The following assessments will occur at the End of study visit:

- 1. Wound evaluation and photograph
- 2. VAS pain scale
- 3. Wound debridement (if applicable)

A wound dressing, if deemed necessary by the investigator will be applied.

5.8 Adjunctive Care:

All patients will receive standard adjunctive therapy for lower extremity ulcerations. Efforts will be made to control any edema by limb elevation, diuretic medication or compression hose, as indicated. Patients will be advised to stay off the affected foot as much as possible, and asked to avoid walking, except as absolutely necessary. Patients will be offered other assistive modalities at the time of enrollment (crutches, canes, and walkers) to enhance postural stability.

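### Section 5.7 places the 20-week end-of-study visit on Day 112, which is week 16; 20 weeks is Day 140

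*Combined protocol and SAP*

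**What the plan says.** Section 5.7 gives the timing of the last visit for patients with unhealed wounds: "At the end of the 20-week evaluation, patients with open wounds will return to clinic on Day 112 (+/- 2 days". For patients who heal or withdraw, the same section says that "the end of study evaluation will take place at the patient's last day of study visit and will occur prior to Day 112". The assessments listed for this visit are wound evaluation with photograph, the VAS pain scale, and debridement where applicable.

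The other sections that state a duration give 20 weeks:

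- Section 3.1, on ulcer size and photographs: "during screening and on all clinic visits up to 20 weeks or when the ulcer is healed, whichever is sooner".
- Section 4.2, study duration: "Up to 20 weeks, sooner pending wound healing as defined by 100% re-epithelialization".
- Section 5.3, inclusion criterion (f), which asks patients to accept "micro water jet technology debridement potentially weekly or biweekly as part of their wound care treatment plan for up to 20 weeks".
- Section 5.6: "Wound will be followed for a total of 20 weeks or when the wound has completely healed".

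The protocol summary repeats the 20-week limit in its length-of-study entry and in three of its efficacy assessments. Day 112 appears only in section 5.7, twice. No section mentions a 16-week period.

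**The concern.** Section 5.7 is the only place that turns the study duration into a study day, so it is the line staff would use to schedule the final visit. Read by its day number, it closes patients with open wounds at week 16. Read with sections 3.1 and 5.6, the same patients are assessed until week 20. Both cannot be done.

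The last wound-size and pain measurements feed the first two primary endpoints in section 3.1, and the patients affected are those whose healing is still undecided. If the two readings were mixed, patients would have unequal follow-up for healing, wound size, pain and infection.

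The second mention of Day 112 adds a further problem. Sections 4.2 and 5.6 allow a wound to heal in weeks 17 to 20, but such a patient cannot have an end-of-study evaluation before Day 112.

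**Working it through.** **Inputs**

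- Visit day 112, window ±2 days: section 5.7.
- Duration 20 weeks: summary and sections 3.1, 4.2, 5.3(f), 5.6 and 5.7.
- Visits every one to two weeks: section 5.6.
- 16 evaluable and 20 enrolled patients: section 8.1.

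**Trying to reproduce Day 112 from 20 weeks** (study day = weeks × 7)

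- First day numbered Day 0: 20 × 7 = Day 140.
- First day numbered Day 1: 20 × 7 + 1 = Day 141.
- Day 112 in weeks: 112/7 = 16.0.
- Days per week needed for 20 weeks to end on Day 112: 112/20 = 5.6.

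The stated figure does not reproduce under either numbering.

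**Could the window explain it?**

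- Around Day 112: 112 ± 2 = Days 110 to 114, or 15.7 to 16.3 weeks.
- Around Day 140: 140 ± 2 = Days 138 to 142.
- Distance between the windows: 138 − 114 = 24 days. They do not overlap.

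**Could a run-in or a different origin explain it?** A shift of 140 − 112 = 28 days would be needed. Section 5.4 treats baseline assessment as part of treatment initiation, and section 5.5 has debridement follow that assessment. No four-week lead-in is described.

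**Size of the conflict**

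- Days: 28/140 = 20% of follow-up.
- Weekly visits after Day 112: Days 119, 126, 133 and 140, so 4 of 20.
- Biweekly visits after Day 112: Days 126 and 140, so 2 of 10.

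**Which number is the odd one out?** The 20-week period is stated 11 times: four in the summary, three in section 3.1, and one each in sections 4.2, 5.3, 5.6 and 5.7 (4 + 3 + 1 + 1 + 1 + 1 = 11). Day 112 is stated twice, both times in section 5.7.

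**Illustration only.** The documents give no healing rate and no support for a constant hazard. If a proportion p20 healed by week 20 under a constant hazard, the proportion healed by week 16 would be 1 − (1 − p20)^(16/20).

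| Assumed healed by week 20 | Healed by week 16 | Difference (points) | Of 16 patients | Of 20 patients |
|---|---|---|---|---|
| 30% | 24.8% | 5.2 | 0.83 | 1.04 |
| 40% | 33.5% | 6.5 | 1.03 | 1.29 |
| 50% | 42.6% | 7.4 | 1.19 | 1.49 |
| 60% | 52.0% | 8.0 | 1.29 | 1.61 |

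On those assumptions the choice of week moves roughly one patient from healed to not healed.

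**The case against.** The discrepancy itself has no defence, but its weight can be argued down.

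- **The count is softer than it looks.** Nine of the 11 statements are upper limits, which a week-16 close would not strictly breach, and several are the same text repeated in summary and body. Only section 5.6 and the opening of section 5.7 fix an end at 20 weeks. This is fair. That Day 112 is the wrong number is an inference, though a strong one. The contradiction does not need the count, because sections 5.6 and 5.7 are enough.
- **Unequal follow-up is possible, not shown.** One team at one centre would probably apply one reading to everyone, and there is no comparator arm to bias. This stands. What remains is that nobody can tell from the protocol which reading applies.
- **The statistical stakes are modest.** This is an exploratory pilot of up to 20 patients. No endpoint in section 3.1 is defined at a fixed week, and section 8.2 names no time-point analysis. This also stands, and it limits the consequence. It does not make the visit instruction workable.
- **The healing figures are hypothetical.** Agreed. The conclusion does not rest on them.

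**Conclusion.** The point holds and must be fixed. Section 5.7 gives two incompatible times for one operative visit, and its rule for healed or withdrawn patients carries the same wrong day. The documented size is 28 days, one fifth of the stated follow-up, and it falls on patients whose wounds are open at week 16. This conclusion needs only calendar arithmetic and the wording of sections 5.6 and 5.7. That 20 weeks is the intended duration is inferred from the rest of the protocol. The effect on the healed proportion cannot be determined from the documents. The planned sample size of 20 does not depend on the visit day.

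**What to change.** In section 5.7, change the visit for open wounds to Day 140 (±2 days). For healed or withdrawn patients, replace the limit of before Day 112 with on or before Day 140. Wording it as no later than the Day 140 (±2 days) visit would be slightly better, because a wound first found healed on Day 141 or 142 is then covered. It would also help to state which day is the origin, for example the first debridement as Day 0, since the protocol does not define one.

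If the sponsor did intend 16 weeks, keep Day 112 and change every 20-week statement: the summary, sections 3.1, 4.2, 5.3(f) and 5.6, and the opening of 5.7. A patient who heals or withdraws should then have the evaluation no later than the Day 112 visit.

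The first option costs two day numbers in one section, with no extra patients and no visits beyond the 20 weeks already stated.
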